10.4 Utility Evaluation

Utility evaluation is the frequency and duration of use of the closed loop system combined with pump suspend feature in the closed-loop treatment arm as well as CGM use in both treatment arms.

10.5 Psychosocial Evaluation

The subjects' response will be assessed in terms of life-style change and daily diabetes management, as evaluated by questionnaires and a semi-structured qualitative interview (only applicable to CL intervention arm and also including family members).

11 Assessment and Reporting of Adverse Events

11.1 Definitions

11.1.1 Reportable Adverse Events

A reportable Adverse Event is any untoward medical occurrence that meets criteria for a serious adverse event or any unanticipated medical occurrence in a study subject that is study or device-related. Device deficiencies that could have led to a serious adverse device effect will also be reported.

11.1.2 Adverse Events

An adverse event (AE) is any untoward medical occurrence, unintended disease or injury, or untoward clinical signs (including abnormal laboratory findings) in a subject who has received an investigational device, whether or not related to the investigational medical device. This definition included events related to the device under investigation or the comparator or to the study procedures. For users or other persons, this definition is restricted to events related to the investigational device.

The following anticipated adverse events will not be recorded:

- Non clinically significant skin reactions as judged by investigator
- Pre-existing medical conditions
- New illnesses or conditions not requiring concomitant medication or medical intervention/procedures
- Non severe hypoglycaemia
- Hyperglycaemia without significant ketonaemia (>0.6mmol/l)

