11.1.3 Adverse Device Effect

An Adverse Device Effect (ADE) is an adverse event related to the use of an investigational medical device. This includes adverse events resulting from insufficient or inadequate instructions for use, deployment, implantation, installation, or operation, or any malfunction of the investigational medical device. This definition also includes any event resulting from use error or from intentional misuse of the device under investigation.

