11.2.2 Recording and Reporting of Adverse Events

Throughout the course of the study, all efforts will be made to remain alert to possible adverse events or untoward findings. The first concern will be the safety of the subject, and appropriate medical intervention will be taken. The investigator will elicit reports of adverse events from the subject at each visit and complete adverse event forms. All AEs, including those the subject reports spontaneously, those the investigators observe, and those the subject reports in response to questions will be recorded on paper or electronic AE forms at each site within seven days of discovering the event.

The study investigator will assess the relationship of any adverse event to be device-related or unrelated by determining if there is a reasonable possibility that the adverse event may have been caused by the study device or study procedures. The individual investigator at each site will be

responsible for managing all adverse events according to local protocols, and decide if reporting is required.

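### The recording exemptions in Protocol 11.1.2 for pre-existing and untreated new conditions make no exception for device-related or worsening events and are not reconciled with 11.2.2 and 14.3

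*Protocol*

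**What the plan says.** Section 11.1.2 defines an adverse event broadly, "whether or not related to the investigational medical device". It then gives a list under the words "The following anticipated adverse events will not be recorded". Two of the five items matter here: "Pre-existing medical conditions" and "New illnesses or conditions not requiring concomitant medication or medical intervention/procedures". The other three concern skin reactions, hypoglycaemia and hyperglycaemia, and each is limited by clinical significance, severity or ketone level.

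Other sections bear on the same events:

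- Section 11.1.1 makes serious events reportable, and also "any unanticipated medical occurrence in a study subject that is study or device-related".
- Section 11.1.3 says: "An Adverse Device Effect (ADE) is an adverse event related to the use of an investigational medical device". It adds malfunction and "any event resulting from use error or from intentional misuse of the device under investigation". It sets no treatment threshold.
- Section 11.2.2 says: "All AEs, including those the subject reports spontaneously, those the investigators observe, and those the subject reports in response to questions will be recorded". It also has the investigator judge, for any adverse event, whether it is device-related.
- Section 14.3 promises a listing of all adverse events over the whole study.

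**The concern.** The two items turn on the wrong test for a device trial. Whether an untreated new condition is recorded depends only on whether it needed treatment, and a pre-existing condition is exempt without any test. Device relatedness and worsening, which decide whether an event is informative about the system, play no part. Sites also receive two instructions, one to leave these events off the form and one to record everything, with no statement of which prevails.

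Safety, including adverse events other than severe hypoglycaemia, is a stated objective (section 5.2). The DSMB reviews compiled adverse event data (sections 11.5 and 17.1), and neither the DSMB nor the 14.3 listing can show what was not recorded. The exemptions apply to both arms, but effects specific to the closed-loop system can arise only in the intervention arm.

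**Working it through.** The point is textual. There is no figure in the plan to reproduce and no calculation to run. The check sets the sections side by side.

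1. **Do the two items carry a limit?** The pre-existing item has none. The new-illness item is limited only by need for treatment. Neither mentions relatedness, and the pre-existing item does not mention worsening.

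2. **Does the word anticipated supply the limit?** Only in part. Sections 11.3.2 to 11.3.7 set out specific anticipated risks: glucose excursions, blood sampling, finger-pricks, pump, sensor and questionnaires. An open class of new illnesses is not among them. Section 11.1.2 thus labels any untreated new condition as anticipated, whatever its nature.

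3. **What does the pre-existing item do in practice?** A stable condition is not an untoward occurrence during the study and would not be an adverse event anyway. The item therefore matters mainly if a site applies it to worsening. Such participants can be enrolled: section 7.3 excludes untreated coeliac disease and hypothyroidism, and active retinopathy, but not treated or inactive forms.

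4. **Compare with 11.2.2.** If all adverse events are recorded, the 11.1.2 list has no effect. If the list prevails, 11.2.2 is wrong as written, and an exempt event has no form on which its relatedness is documented. The text does not choose.

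5. **Compare with 14.3.** The listing can hold only what was recorded. Under the list, a listing described as complete would omit the exempt events.

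6. **Trace one event.** Take a non-serious new symptom that the investigator thinks was caused by the device and that settles without treatment. Under 11.1.3 it is an adverse device effect. Under 11.2.2 it is recorded and its relatedness assessed. Under 11.1.2 it is not recorded.

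7. **What remains captured whichever section prevails?** All serious events are reported, related or not and anticipated or not (11.2.5), and the serious-event definition includes serious deterioration in health (11.1.4). Severe hypoglycaemia and DKA need serious-event forms, and severe hyperglycaemia with raised ketones is an adverse event (11.2.3, 11.2.4). Severe skin reactions need a form (11.3.6). Device deficiencies are documented (11.2.6), apart from a short exempt list (11.1.7).

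The exposed set is therefore non-serious, untreated, device- or procedure-related new events outside these routes, and non-serious worsening of existing conditions.

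**The case against.** The strongest case against the point has five parts.

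- **Scope.** The list covers anticipated events, while the non-serious limb of 11.1.1 covers unanticipated ones. Read literally they do not overlap. This stands against any claim that 11.1.2 plainly overrides 11.1.1. It does not remove the ambiguity, because an untreated new illness is called anticipated by label alone.
- **Ordinary drafting.** A specific exception to a general recording rule is common, and 11.1.3 is a definition, not a recording rule. Both remarks are fair. But 11.2.2 and 14.3 say all without referring to an exception, and a relatedness assessment for any adverse event is hard to square with not recording some of them.
- **Other routes.** Serious events, device deficiencies, ketone-positive hyperglycaemia and severe skin reactions are captured elsewhere, and glucose excursions are measured by CGM as endpoints. This stands and narrows the gap considerably.
- **Worsening.** A worsening can be read as a new untoward occurrence and hence recordable. That reading is reasonable, but the protocol does not state it, so sites may differ.
- **Equal exemptions.** Both arms have the same exemptions and use the same pump model and sensor, and the formal safety comparisons in 14.3 use outcomes that are not exempt. This stands. Uneven loss is possible only for effects specific to the closed-loop system, and it would affect the adverse event listing, not those comparisons.

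A reader might infer that 11.1.2 bars the recording of device effects and that reportable ones are never captured. The documents do not support that: serious events are always reported, 11.2.2 orders all adverse events to be recorded, and the heading of the list limits its scope.

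**Conclusion.** The point holds as an unreconciled conflict with a risk of under-recording. Two exemptions in 11.1.2 lack a qualifier for relatedness or worsening, and they are not aligned with 11.2.2 or 14.3. A site that follows 11.1.2 could leave out non-serious, untreated, device-related events and non-serious worsening of existing conditions. This assumes that some sites would treat the list as the operative instruction; the text permits that but does not compel it.

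The number of events affected cannot be stated, because the protocol gives no rate for them. A reader might multiply out the exposure: 84 randomised / 2 = 42 closed-loop participants, and 42 × 84 days = 3,528 participant-days. That is planned exposure, not events lost, and it assumes equal allocation, which sections 7.4 and 9.6 do not state.

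The primary endpoint and the formal safety comparisons are unaffected. The correction still matters, because it determines which device-related events reach the adverse event listing and the DSMB.

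**What to change.** Make three changes of wording.

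1. In 11.1.2, limit both items to non-serious events judged unrelated to the study devices or procedures, so that any event judged related is recorded whether or not it was treated.
2. In 11.1.2, state that worsening of a pre-existing condition is an adverse event.
3. In 11.2.2 and 14.3, replace the unqualified references to all adverse events with a reference to the set recorded under the revised 11.1.2, so that recording, relatedness assessment and listing cover the same events.

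The cost is a protocol wording change and a few more adverse event forms at the sites. Design, sample size and efficacy analysis do not change.

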11.1.3 Adverse Device Effect

An Adverse Device Effect (ADE) is an adverse event related to the use of an investigational medical device. This includes adverse events resulting from insufficient or inadequate instructions for use, deployment, implantation, installation, or operation, or any malfunction of the investigational medical device. This definition also includes any event resulting from use error or from intentional misuse of the device under investigation.

11.1.4 Serious Adverse Event

A serious adverse event (SAE) is an adverse event that:

- led to a death
- led to a serious deterioration in the health of the subject, that either resulted in:
 - a life threatening illness or injury
 - a permanent impairment of a body structure or function

- in-patient hospitalisation or prolonged hospitalisation
- medical or surgical intervention to prevent life-threatening illness or injury or permanent impairment to a body structure or a body function
- led to foetal distress, foetal death or a congenital abnormality or birth defect

A planned hospitalization for pre-existing condition, or a procedure required by the study protocol, without a serious deterioration in health, is not considered to be a serious adverse event.

More than one of the above criteria can be applicable to one event. Life-threatening in the definition of a serious adverse event or serious adverse reaction refers to an event in which the subject was at risk of death at the time of the event; it does not refer to an event which hypothetically might have caused death if it were more severe. Medical judgement should be exercised in deciding whether an adverse event or reaction is serious in other situations.

Important adverse events or reactions that are not immediately life-threatening or do not result in death or hospitalisation but may jeopardise the subject or may require intervention to prevent one of the other outcomes listed in the definition above, should also be considered serious.

The following serious adverse events, should they occur, will be classified as anticipated:

- Severe hypoglycaemia
- DKA

11.1.5 Serious Adverse Device Effect

A Serious Adverse Device Effect (SADE) is an adverse device effect that has resulted in any of the consequences characteristic of a serious adverse event.

11.1.6 Unanticipated Serious Adverse Device Effect

An Unanticipated Serious Adverse Device Effect (USADE) is a serious adverse device effect which by its nature, incidence, severity or outcome has not been identified in the current version of the protocol.

This includes unanticipated procedure related serious adverse events; that is, serious adverse events occurring during the study procedure that are unrelated to any malfunction or misuse of the investigational medical device.

An Anticipated Serious Adverse Device Effect (ASADE) is a serious adverse device effect which by its nature, incidence, severity or outcome has been identified in the protocol.

11.1.7 Device Deficiencies

A device deficiency is an inadequacy of a medical device with respect to its identity, quality, durability, reliability, safety or performance. A device deficiency may lead to an Adverse Device Effect or Serious Adverse Device Effect. The following anticipated device deficiencies and device-related issues will not be recorded:

- Infusion set occlusion/leakage not leading to ketonaemia
- Sensor failure due to miscalibration/detachment
- Premature interruption of sensor-life
- Battery lifespan deficiency due to inadequate charging or extensive wireless communication
- CAD error messages not needing system replacement
- Intermittent device communication failure not leading to system replacement

11.1.8 Adverse Event Intensity

Intensity	Definition
Mild	Patient is aware of signs and symptoms but they are easily tolerated
Moderate	Signs / symptoms cause sufficient discomfort to interfere with usual activities
Severe	Patient is incapable to work or perform usual activities

NB. The term “severe” is often used to describe the intensity (severity) of a specific event. This is not the same as ‘serious’, which is based on patient/event outcome or action criteria (see definition 11.1.4). For example, itching for several days may be rated as severe, but may not be clinically serious.

11.1.9 Adverse Event Causality

Intensity	Definition
Not assessable	A report suggesting an adverse event, which cannot be judged because information is insufficient or contradictory, and which cannot be supplemented or verified.
Unlikely	A clinical event, including laboratory test abnormality, with a temporal relationship, which makes a causal relationship improbable, and in which other drugs/treatments, chemicals or underlying disease(s) provide plausible explanations.
Possible	A clinical event, including laboratory test abnormality, with a reasonable time sequence to administration of the treatment/use of investigational treatment/device, but which also could be explained

	by concomitant diseases or other drugs/treatments or chemicals.
Probable	A clinical event, including laboratory test abnormality, with a reasonable time sequence to administration of the treatment/use of medical method/device, unlikely to be attributable to concomitant disease(s) or other drugs/treatments or chemicals, and which follows a clinically reasonable response on withdrawal (dechallenge). Rechallenge information is not required to fulfil this definition.
Definite/certain	A clinical event, including laboratory test abnormality, occurring in a plausible time relationship to study treatment/use of medical method/device and which cannot be explained by concomitant disease(s), other drugs/treatments or chemicals. The response to withdrawal of the treatment (dechallenge) should be clinically plausible. The event must be unambiguous, either pharmacologically or as phenomenon, using satisfactory rechallenge procedures if necessary.

(Reference: WHO-UMC Causality Categories)

11.2 Recording and Reporting of Adverse Events, Serious Adverse Events and Device Deficiencies

11.2.1 Monitoring Period of Adverse Events

The period during which adverse events will be reported is defined as the period from the beginning of the study (obtaining informed consent) until 3 weeks after the end of the study participation. Adverse events that continue after the subject's discontinuation or completion of the study will be followed until their medical outcome is determined or until no further change in the condition is expected. The follow up of AEs may therefore extend after the end of the clinical investigation; however no new AEs will be reported after the trial reporting period.

11.2.2 Recording and Reporting of Adverse Events

Throughout the course of the study, all efforts will be made to remain alert to possible adverse events or untoward findings. The first concern will be the safety of the subject, and appropriate medical intervention will be taken. The investigator will elicit reports of adverse events from the subject at each visit and complete adverse event forms. All AEs, including those the subject reports spontaneously, those the investigators observe, and those the subject reports in response to questions will be recorded on paper or electronic AE forms at each site within seven days of discovering the event.

The study investigator will assess the relationship of any adverse event to be device-related or unrelated by determining if there is a reasonable possibility that the adverse event may have been caused by the study device or study procedures. The individual investigator at each site will be

responsible for managing all adverse events according to local protocols, and decide if reporting is required.

11.2.3 Severe Hypoglycaemia

In adult subjects, severe hypoglycaemia will be defined as an event requiring assistance, which means that assistance of another person is needed to actively administer carbohydrate, glucagon, or other resuscitative actions. These episodes may be associated with sufficient neuroglycopenia to induce seizure or coma.

In paediatric subjects hypoglycaemic events will be considered severe if the event requires assistance of another person due to altered consciousness to actively administer carbohydrate, glucagon, or other resuscitative actions. This means that the subject is impaired cognitively to the point that he/she is unable to treat him- or herself, is unable to verbalize his or her needs, is incoherent, disoriented, and/or combative, or experiences seizure or coma. If plasma glucose measurements are not available during such an event, neurological recovery attributable to the restoration of plasma glucose to normal is considered sufficient evidence that the event was induced by a low plasma glucose concentration.

Severe hypoglycaemia will be regarded as a foreseeable serious adverse event and a serious adverse event form will be completed. Non-severe hypoglycaemia will not be reported or considered an adverse event.

11.2.4 Hyperglycaemia, Ketonemia and Diabetic Ketoacidosis

Diabetic Ketoacidosis (DKA) is defined as: hyperglycemia (blood glucose >250 mg/dl or >13.9 mmol/l) with either low serum bicarbonate (<15 mEq/l) and/or low pH (<7.24), anion gap (> 12) and either ketonemia or ketonuria and requiring treatment within a health-care facility (American Diabetes Association Workgroup on Hypoglycemia, Diabetes Care 28:1245-1249, 2005).

DKA will be regarded as a foreseeable serious adverse event and a severe adverse event form will be completed.

Severe hyperglycaemic events (fingerprick glucose >300 mg/dl/16.7mmol/l and blood ketones >0.6mmol/l) will be recorded as Adverse Events. Non-severe hyperglycaemia events will not be reported or considered as adverse events.

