11.2.5 Reporting of Serious Adverse Events and Serious Adverse Device Effects

When reporting adverse events, all pertinent data protection legislation must be adhered to.

The serious adverse event report should contain the following information*:

1. Study identifier (EudraCT number if applicable)
2. Participant's unique study number
3. Date of birth
4. Event description
5. Start date of event
6. Laboratory tests used and medical interventions used to treat the SAE
7. Planned actions relating to the event, including whether the study device was discontinued
8. Statement on the patient's current state of health
9. Reason for seriousness (i.e. death, life threatening, hospitalisation, disability/incapacity or other)
10. Evaluation of causality (including grade of relatedness) with the following (more than one may apply):
 - a. the investigational treatment/medical device
 - b. the clinical study/a study specific procedure
 - c. other: e. g. concomitant treatment, underlying disease
11. Reporter's name, date and signature

*In the case of incomplete information at the time of initial reporting, all appropriate information should be provided as soon as this becomes available.

The relationship of the SAE to the investigational treatment / medical device should be assessed by the investigator at site, as should the anticipated or unanticipated nature of any SAEs and SADEs. All SAEs whether or not deemed investigational method/device related and whether anticipated or unanticipated must be reported to the Sponsor by email or fax within 24 hours (one working day) of the Investigator learning of its occurrence.

UK specific reporting instructions:

SAEs should be reported to:

[name]
Cambridge University Hospitals
NHS Foundation Trust
Box 277, Addenbrooke's Hospital
[name], UK
[contact]
[contact]
E-mail: r&[contact]

A written report must follow within five working days and is to include a full description of the event and sequelae, in the format detailed on the Serious Adverse Event reporting form. If applicable, the Sponsor will notify the competent authority of all Serious Adverse Events in line with pertinent legal requirements.

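### The exclusion of non-severe hypoglycaemia and hyperglycaemia from adverse event reporting has no exception for events that are serious, and so contradicts the protocol's own SAE rule

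*Protocol*

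**What the plan says.** **The exclusions.** Protocol section 11.2.3 states: "Non-severe hypoglycaemia will not be reported or considered an adverse event". Section 11.2.4 states: "Non-severe hyperglycaemia events will not be reported or considered as adverse events". Section 11.1.2 has a list of anticipated adverse events that will not be recorded. It includes non-severe hypoglycaemia, and hyperglycaemia without ketonaemia above 0.6 mmol/l. None of the three places carries a condition or exception.

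**The general rule.** Section 11.1.1 states: "A reportable Adverse Event is any untoward medical occurrence that meets criteria for a serious adverse event". It also covers unanticipated events related to the study or device. Section 11.1.4 begins: "A serious adverse event (SAE) is an adverse event that". Among the results of a serious deterioration in health it lists "in-patient hospitalisation or prolonged hospitalisation". Its only carve-out for admissions is "A planned hospitalization for pre-existing condition, or a procedure required by the study protocol, without a serious deterioration in health". Section 11.2.5 adds: "All SAEs whether or not deemed investigational method/device related and whether anticipated or unanticipated must be reported to the Sponsor", within 24 hours.

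**What is kept.** Section 11.2.3 says: "Severe hypoglycaemia will be regarded as a foreseeable serious adverse event and a serious adverse event form will be completed". Section 11.2.4 treats DKA in the same way. It also records severe hyperglycaemia as an adverse event, which needs both fingerprick glucose above 16.7 mmol/l and blood ketones above 0.6 mmol/l.

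**The concern.** In sections 11.2.3 and 11.2.4, severe is defined by the clinical picture or by a glucose and ketone pair. In section 11.1.4, serious is defined by outcome. The two do not nest: an event can be non-severe by the first test and serious by the second. For such an event one part of the protocol says report it and another says it is not an adverse event at all.

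Safety is a stated objective (section 5.2), and low and high glucose are the harms most closely tied to automated insulin delivery with pump suspension. The SAE label is what starts notification of the sponsor and regulator (section 11.2.5) and of the DSMB (sections 11.5 and 17.1). The trial is open-label and runs at six centres in two countries, with separate UK and US reporting instructions. Section 11.2.2 leaves each site's investigator to judge whether an event must be reported. The same admission could therefore be an SAE at one centre and leave no record at another.

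**Working it through.** No arithmetic applies, and the protocol gives no figure to reproduce. The check sets the definitions side by side and asks which events fall between them.

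**Step 1: events that are safely captured.** Severe hypoglycaemia and DKA are SAEs by name. Hyperglycaemia with glucose above 16.7 mmol/l and blood ketones above 0.6 mmol/l is an adverse event, so section 11.1.4 can make it serious. No conflict arises for these.

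**Step 2: events left over.** Take admissions that result from a serious deterioration in health.

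| Event | Section 11.1.2 list | Sections 11.2.3 / 11.2.4 | Section 11.1.1 |
|---|---|---|---|
| Glucose above 16.7 mmol/l, blood ketones at most 0.6 mmol/l, no acidosis | Not recorded | Not an adverse event | Reportable |
| Same, ketones not measured | Unclear | Cannot be shown to be severe | Reportable |
| Ketones above 0.6 mmol/l, glucose at most 16.7 mmol/l, DKA criteria not met | Not on the list | Not an adverse event | Reportable |
| Hypoglycaemic child without the cognitive impairment described in section 11.2.3 | Not recorded | Not an adverse event | Reportable |

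The second row can occur under the protocol's own procedures. Section 10.3 asks for ketones on waking when fingerprick glucose is above 14 mmol/l, and accepts a blood or a urine test. A urine result cannot supply the blood ketone value that section 11.2.4 needs.

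**Step 3: does the 24-hour duty rescue them?** Section 11.2.5 applies to SAEs. Section 11.1.4 defines an SAE as a kind of adverse event. If sections 11.2.3 and 11.2.4 deny that the event is an adverse event, then read literally it cannot be an SAE, and the duty is not triggered. Section 11.1.1 starts instead from an untoward medical occurrence and looks only at the seriousness criteria. So the collision is between section 11.1.1 and sections 11.2.3 and 11.2.4. No section states an order of precedence.

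**Step 4: other signs that these sections were not reconciled.**
- Section 11.1.2 calls the excluded events adverse events that are not recorded. Sections 11.2.3 and 11.2.4 say that they are not adverse events.
- Section 11.1.2 excludes hyperglycaemia on ketones alone. Section 11.2.4 uses glucose and ketones together, which produces the third row.
- For adults and adolescents, exclusion criterion 8 in section 7.3 counts an episode leading to hospital attendance as severe hypoglycaemia. Section 11.2.3 does not mention attendance.

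**The case against.** The strongest reply is that the protocol already has routes by which these events are reported. Section 11.1.1 turns on the seriousness criteria and not on adverse event status, so an investigator who follows it reports the admission. Section 11.1.2 itself calls the events adverse events, section 11.1.4 asks for medical judgement on seriousness, and section 11.2.5 covers anticipated SAEs as well as unanticipated ones. Section 11.2.6 separately requires any device deficiency that might have led to a serious adverse device effect to go to the sponsor.

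Much of this stands. A reader might infer that glucose-related admissions simply drop out of safety reporting. The documents do not support that: section 11.1.1 gives a valid route, and what is missing is the rule that says it prevails. The device deficiency route is only a partial help. It covers admissions where a deficiency is identified, and the list of unrecorded deficiencies in section 11.1.7 includes an infusion set blockage that does not lead to ketonaemia.

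Three further limits also stand:
- **Seriousness.** Hospitalisation counts in section 11.1.4 only when it results from a serious deterioration in health, so an admission for observation alone need not qualify.
- **Low glucose.** The paediatric definition in section 11.2.3 covers children who are conscious but disoriented, incoherent or unable to treat themselves. In adults, any need for another person's active help is enough. The gap is therefore narrower for low glucose than for high glucose.
- **Results.** A reader might infer that the between-arm safety comparison is altered. Section 14.3 tabulates by group only DKA, severe hypoglycaemia and severe hyperglycaemia, and none of these counts changes. Other adverse events are listed.

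**Conclusion.** The contradiction is real and should be removed. The exclusions in sections 11.1.2, 11.2.3 and 11.2.4 are unconditional, section 11.1.1 requires the opposite for serious events, and nothing ranks them. The consequence is that a residual group of serious glucose-related admissions can be missed or handled inconsistently, depending on which section a site follows. It is not established that they would be lost.

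The effect is confined to AE and SAE listings and to notification of the sponsor, regulator and DSMB. The primary endpoint, the secondary endpoints and the tabulated safety outcomes are untouched.

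No frequency can be given. The documents contain no rate for admissions outside the three definitions and no indication of how sites would read the sections. An expected number of lost events would need an outside rate and the assumption that every such event goes unreported, and the documents support neither. The conclusion rests on the wording alone and needs no rate.

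**What to change.** Reconcile sections 11.1.1, 11.1.2, 11.1.4, 11.2.3, 11.2.4 and 11.2.5. Add one sentence to the non-recording list in section 11.1.2 and to sections 11.2.3 and 11.2.4: these exclusions do not apply when an event meets any seriousness criterion in section 11.1.4, in which case it is recorded and reported as an SAE under section 11.2.5, whatever the glucose, ketone or consciousness findings.

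The definitions of severe hypoglycaemia, severe hyperglycaemia and DKA used as outcomes stay unchanged. In the same edit, settle whether the excluded events are unrecorded adverse events (section 11.1.2) or not adverse events (sections 11.2.3 and 11.2.4), and reconcile the mention of hospital attendance in section 7.3 with section 11.2.3.

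The cost is one sentence in three places, a note to sites and at most a few extra SAE forms. Endpoints, sample size and analysis do not change.
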